Visit window	NA	-	± 3 d	± 3 d	± 3 d	± 3 d	± 1 wk	± 1 wk	± 1 wk	± 1 wk
Informed consent	X									
Demography	X									
Medical and surgical history ⁷	X									
Eligibility	X	X								
Tumor biopsy ⁸	X				X ³¹					
Performance (ECOG) status ⁹	X	X	X	X		X ³²	X	X	X	X
Height ⁹	X									
Weight ⁹	X	X	X	X		X ³²	X	X		
Physical examination ⁹	X	X	X	X		X ³²	X	X	X	
Vital signs ¹⁰	X				PRE- & 15m, 30m, 1h, 2h, 4h POST-dose		X	X		
Electrocardiogram ¹¹	X	PRE- & 30 min POST-dose	PRE- & 30 min POST-dose	PRE- & 30 min POST-dose		X ³²				
Hematology and biochemistry ¹²	X	X		X		X ³²	X			
Creatinine clearance ¹³	X	X	X							
Coagulation ¹²	X	X	X	X		X ³²				

List of footnotes

1. Re-screening may be allowed on a case-by-case basis. In the case of out-of-range laboratory results during the screening period, a re-test may be allowed within the screening period. The investigator must contact the medical monitor to discuss each re-screening case.
2. The EoT visit will be done within 7 days after the subject is taken off CyPep-1.

3. The FU visit will occur at least 30 days after the last CyPep-1 or pembrolizumab (combination arm) administration (if the EoT visit occurs more than 30 days after the last treatment administration, the FU visit will be skipped).
4. For subjects who leave the trial early and do not receive any other anti-cancer therapy or any other investigational therapy, PFS visits should continue to be performed every 8 weeks (from D1) until occurrence of confirmed progressive disease (PD) or until start of any further line of anticancer treatment.
5. Every 3 months after confirmed PD and until the end of the trial, by phone call. In case of unconfirmed PD (iUPD) by iRECIST and subject has started further line of anti-cancer treatment, the first OS-FU visit will be done 90 days after the iUPD event occurred. Besides overall survival status, any next line of anti-cancer therapies, ORR and duration of response to next line anti-cancer therapies, and additional relevant information will be recorded. If necessary, patients may be contacted occasionally outside of this FU window, and data regarding next line anti-cancer therapies can be collected, retrospectively.
6. Additional cycles of CyPep-1 are planned with continued Q2W administration, please see [Table 1 b/e](#) for schedule of assessments (in this case, end of treatment [EoT], FU, PFS-FU, and OS-FU are relative to each cycle).

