13.2 APPENDIX 2. CENSORING RULES: DOR and PFS

Censoring rules for DOR and PFS are presented in [Table 8](#) below.

Table 8. Censoring Rules for DOR and PFS

#	Situation	Date of Event (PD/Death) or Censoring	Outcome: Event (PD/Death) or Censored
1	No (or inadequate) baseline tumor assessments and the subject has not died	Treatment Start Date	Censored
2	No post-baseline assessments and the subject has not died	Treatment Start Date	Censored
3	iUPD followed by discontinuation due to clinical disease progression, radiological disease progression or death within 8 weeks	Date of assessment of progression ¹	Event
4	iUPD without subsequent iSD, iPR or iCPD and followed by:	Date of assessment of progression ¹	Event
	1. Treatment discontinuation due to clinical instability (i.e., clinical disease progression, radiological disease progression). 2. No further response assessments (due to subject refusal, protocol non-compliance, or subject death). 3. Next timepoint responses all equal to iUPD. 4. Subject death from cancer.		
5	No iUPD as described in #3 and #4, no iCPD or death and no new protocol excluded anticancer treatment documented	Date of last 'adequate' assessment of response ²	Censored
6	No iUPD as described in #3 and #4, no iCPD or death and new protocol excluded anticancer treatment documented	Date of last 'adequate' assessment of response ² on or prior to starting anticancer therapy	Censored
7	New protocol excluded anticancer treatment started (prior to iUPD as described in #3 and #4, iCPD or death) ³	Date of last 'adequate' assessment of response ² on or prior to starting anticancer therapy	Censored
8	iCPD documented between scheduled visits	Date of assessment of progression ¹	Event
9	Death before first iCPD assessment	Date of death	Event
10	Death between adequate assessment visits	Date of death	Event
11	Death or progression after two missed visits (with 1-week window) where last assessment is not iUPD	Date of last 'adequate' assessment of response ² prior to missed assessments	Censored

¹The earliest of

- (i) Date of radiological assessment showing new lesion (if progression is based on new lesion); or
- (ii) Date of radiological assessment showing unequivocal progression in non-target lesions, or
- (iii) Date of last radiological assessment of measured lesions (if progression is based on increase in sum of measured lesions).

²An adequate assessment is defined as a radiological assessment where iCR, iPR, or iSD was determined.

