13.3 APPENDIX 3. CENSORING RULES: DURATION OF STABLE DISEASE

Censoring rules for duration of stable disease are presented in [Table 9](#) below.

Table 9. Censoring Rules for Duration of Stable Disease

#	Situation	Date of Event (PD) or Censoring	Outcome: Event (PD) or Censored
1	No (or inadequate) baseline tumor assessments and the patient has not died	Treatment Start Date	Censored
2	No post-baseline assessments	Treatment Start Date	Censored
3	iUPD followed by discontinuation due to clinical disease progression, radiological disease progression or death within 8 weeks	Date of assessment of progression ¹	Event
4	iUPD without subsequent iSD, iPR or iCPD and followed by:	Date of assessment of progression ¹	Event
	1. Treatment discontinuation due to clinical instability (i.e., clinical disease progression, radiological disease progression). 2. No further response assessments (due to subject refusal, protocol non-compliance). 3. Next timepoint responses all equal to iUPD.		
5	iCPD documented between scheduled visits	Date of assessment of progression ¹	Event
6	No iUPD as described in #3 and #4, no iCPD and no new protocol excluded anticancer treatment documented	Date of last 'adequate' assessment of response ²	Censored
7	No iUPD as described in #3 and #4, no iCPD and new protocol excluded anticancer treatment documented	Date of last 'adequate' assessment of response ² on or prior to starting anticancer therapy	Censored
8	New protocol excluded anticancer treatment started (prior to iUPD as described in #3 and #4, iCPD) ³	Date of last 'adequate' assessment of response ² on or prior to starting anticancer therapy	Censored
9	Death before first iCPD assessment	Date of last 'adequate' assessment of response ²	Censored
10	Progression after two missed visits (with 1-week window) where last assessment is not iUPD	Date of last 'adequate' assessment of response ² prior to missed assessments	Censored

¹The earliest of

- (i) Date of radiological assessment showing new lesion (if progression is based on new lesion); or
- (ii) Date of radiological assessment showing unequivocal progression in non-target lesions, or
- (iii) Date of last radiological assessment of measured lesions (if progression is based on increase in sum of measured lesions).

²An adequate assessment is defined as a radiological assessment where iCR, iPR, or iSD was determined.

Statistical Analysis Plan

SMS-0571/CyPep-1
V3.0 Final
04-Jun-2024

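### An unconfirmed progression followed by new anticancer therapy can be censored before the progression, because the no-further-scan item in SAP Tables 8 and 9 does not list new therapy

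*SAP*

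**What the plan says.** **Table 8 (SAP Appendix 2, PFS and DOR).** An iUPD that is never confirmed counts as an event, dated at the iUPD, in these situations:

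- Row 3: "iUPD followed by discontinuation due to clinical disease progression, radiological disease progression or death within 8 weeks".
- Row 4, item 1: "Treatment discontinuation due to clinical instability (i.e., clinical disease progression, radiological disease progression".
- Row 4, item 2: "No further response assessments (due to subject refusal, protocol non-compliance, or subject death".
- Row 4, item 3: all later assessments are again iUPD.
- Row 4, item 4: "Subject death from cancer".

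Two rows censor for new therapy. Row 6 applies to "No iUPD as described in #3 and #4, no iCPD or death and new protocol excluded anticancer treatment documented". Row 7 applies to "New protocol excluded anticancer treatment started (prior to iUPD as described in #3 and #4, iCPD or death". Both go back to the last adequate assessment, which footnote 2 of the table limits to iCR, iPR or iSD. Footnote 3 settles a same-day clash with new therapy for iCPD only.

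**Table 9 (SAP Appendix 3, duration of stable disease).** Row 4, item 2 is shorter: "No further response assessments (due to subject refusal, protocol non-compliance". There is no item for cancer death. Rows 7 and 8 censor for new therapy, and row 9 censors deaths.

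**Protocol.** Footnote 5 of the Schedule of Assessments foresees the path: "In case of unconfirmed PD (iUPD) by iRECIST and subject has started further line of anti-cancer treatment". Such a subject goes to survival calls. Footnote 4 and Section 6.2 (Survival) end PFS assessments once a further line of treatment starts. Section 4.3.1 keeps subjects who stop CyPep-1 for safety reasons in follow-up.

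**The concern.** When a subject moves from iUPD to new therapy, the confirmatory scan is missing because the protocol ends scanning. That is neither refusal nor non-compliance, so item 2 of row 4 does not cover it. If no other item applies, the iUPD is not of the kind described in rows 3 and 4, and the new-therapy rows censor the subject at a scan before the iUPD.

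This censoring is informative: the subject leaves the risk set because the disease appeared to progress. It lengthens PFS, DOR and duration of stable disease. It also makes the outcome depend on how the discontinuation reason is recorded and on whether the subject was still on treatment when the iUPD was seen.

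**Working it through.** No figure in the plan depends on these rules, so there is nothing to reproduce. The check applies the rows to one record and then shows the direction of the effect.

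**Inputs.** Scans every 8 weeks (protocol synopsis). Time in months = (date − treatment start + 1) / 30.4375 (SAP 10.1.4 and 10.2.2). Week 8 is day 57 and week 16 is day 113.

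**Record (assumed).** iSD on day 57, iUPD on day 113, new therapy in week 18, no further scan.

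- Event at the iUPD: 113 / 30.4375 = 3.71 months.
- Censored at the last adequate scan: 57 / 30.4375 = 1.87 months.

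| Situation | Table 8 (PFS) | Table 9 (stable disease) |
|---|---|---|
| (a) On treatment; stopped after iUPD, progression recorded | Event, 3.71 (row 3 or item 4.1) | Event, 3.71 (row 3 or item 4.1) |
| (b) On treatment; another reason recorded | Censored, 1.87 (row 6 or 7) | Censored, 1.87 (row 7 or 8) |
| (c) Already off treatment, e.g. for toxicity, and in PFS follow-up | Censored, 1.87 (row 6 or 7) | Censored, 1.87 (row 7 or 8) |
| (d) As (b) or (c), cancer death more than 8 weeks after iUPD | Event, 3.71 (item 4.4) | Censored, 1.87 |

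In (d), rows 6 and 7 of Table 8 do not compete with item 4.4. Row 6 requires that there be no such iUPD and no death. Row 7 requires therapy to start before an iUPD of the row 3 or 4 kind, and here the iUPD came first. Before that death is recorded, though, the same scans give the censored result. The PFS outcome at week 16 therefore depends on later survival follow-up.

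**DOR.** Take iPR at week 8, iPR again at week 16, iUPD at week 24 (day 169), then new therapy. An event gives (169 − 57 + 1) / 30.4375 = 3.71 months. Censoring at week 16 gives (113 − 57 + 1) / 30.4375 = 1.87 months.

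**First post-baseline scan is the iUPD.** Row 2 does not apply, because an assessment exists. Rows 6 and 7 need a post-baseline iCR, iPR or iSD, and there is none. The censoring date is undefined.

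**Direction (assumed data, n = 15).** Progressions: 5 on day 57, 6 on day 113, 4 on day 169. Let k of the six day-113 subjects be censored at day 57. The Kaplan-Meier estimate at day 113 is (10/15) × 4/(10 − k).

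| k | PFS at day 113 |
|---|---|
| 0 | 26.7% |
| 1 | 29.6% |
| 2 | 33.3% |
| 3 | 38.1% |
| 4 | 44.4% |

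The shift is always upward. The values of k are illustrative only.

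**The case against.** The strongest reply is that the gap is narrow. The planned course after iUPD is to stay on treatment and rescan about 4 weeks later (protocol Section 6.2), and footnote 5 only times a phone call for those who leave that course. A subject who does switch will usually stop CyPep-1 with progression recorded, which is already an event. For PFS and DOR, item 4.4 recovers many of the rest, with no time limit. PFS is exploratory, DOR and duration of stable disease are descriptive, and no test, sample size or expansion decision uses these tables. All of this stands, and it limits the reach of the point.

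A reader might infer from item 4.2 that every subject who goes from iUPD to new therapy is censored early. The documents do not support that: situations (a) and (d) are PFS events. A reader might also take the illustration as an estimate of bias in this trial. Nothing in the documents gives the share of subjects in situations (b) and (c), and the illustration makes no allowance for later cancer deaths.

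Three ways of closing the gap by interpretation do not work:

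- Item 4.3 could be called satisfied when there is no later scan, but item 4.2 would then have no purpose.
- Row 3 says discontinuation without naming treatment, so leaving the study might count. A subject who switches therapy stays in the study for survival calls, so this rarely helps.
- The definitions in SAP 10.1.2 and 10.2.2 ask for confirmation or death, and 10.1.4 for confirmation. They are stricter than the tables.

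Nor does Table 9 simply repeat Table 8. It omits death from item 4.2 and has no item 4.4, so its gap is wider.

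**Conclusion.** The point holds in limited form. An unconfirmed iUPD followed by new therapy and no further scan is not an event when the subject was already off study treatment or the discontinuation was not recorded as progression. It is then censored at a scan before the iUPD, or at no defined date if the iUPD was the first post-baseline scan. For PFS and DOR a later cancer death reverses this. For duration of stable disease it does not; only a death within the 8 weeks of row 3 could count.

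Each affected subject in the worked record loses an event at 3.71 months and is censored at 1.87. The direction is known: the estimates become longer. The size in this trial cannot be determined from the documents. Because the endpoints are descriptive and the arms small, this should be corrected before the final analysis, but it does not threaten the trial's primary conclusions. The reading assumes that item 4.2's reasons are a complete list, as the wording suggests.

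**What to change.** Make four changes, in both tables:

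1. In row 4, item 2, add *or start of new anticancer therapy* to the reasons.
2. State that the new-therapy censoring rows (6 and 7 in Table 8, 7 and 8 in Table 9) apply only when the last assessment on or before the start of new therapy is not an iUPD.
3. State that assessments after the start of new therapy are not used for these endpoints. Without this, a subject with iUPD, new therapy and then a recorded iSD would fit neither row 4 nor the restricted censoring rows.
4. Keep the event date at the iUPD date.

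The cost is a few words in two tables. No new data are needed: iUPD dates and new anticancer therapy are already collected. PFS, DOR and duration of stable disease may come out slightly shorter. The change should be made before database lock.

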13.3 APPENDIX 3. CENSORING RULES: DURATION OF STABLE DISEASE

Censoring rules for duration of stable disease are presented in [Table 9](#) below.

Table 9. Censoring Rules for Duration of Stable Disease

#	Situation	Date of Event (PD) or Censoring	Outcome: Event (PD) or Censored
1	No (or inadequate) baseline tumor assessments and the patient has not died	Treatment Start Date	Censored
2	No post-baseline assessments	Treatment Start Date	Censored
3	iUPD followed by discontinuation due to clinical disease progression, radiological disease progression or death within 8 weeks	Date of assessment of progression ¹	Event
4	iUPD without subsequent iSD, iPR or iCPD and followed by:	Date of assessment of progression ¹	Event
	1. Treatment discontinuation due to clinical instability (i.e., clinical disease progression, radiological disease progression). 2. No further response assessments (due to subject refusal, protocol non-compliance). 3. Next timepoint responses all equal to iUPD.		
5	iCPD documented between scheduled visits	Date of assessment of progression ¹	Event
6	No iUPD as described in #3 and #4, no iCPD and no new protocol excluded anticancer treatment documented	Date of last 'adequate' assessment of response ²	Censored
7	No iUPD as described in #3 and #4, no iCPD and new protocol excluded anticancer treatment documented	Date of last 'adequate' assessment of response ² on or prior to starting anticancer therapy	Censored
8	New protocol excluded anticancer treatment started (prior to iUPD as described in #3 and #4, iCPD) ³	Date of last 'adequate' assessment of response ² on or prior to starting anticancer therapy	Censored
9	Death before first iCPD assessment	Date of last 'adequate' assessment of response ²	Censored
10	Progression after two missed visits (with 1-week window) where last assessment is not iUPD	Date of last 'adequate' assessment of response ² prior to missed assessments	Censored

¹The earliest of

- (i) Date of radiological assessment showing new lesion (if progression is based on new lesion); or
- (ii) Date of radiological assessment showing unequivocal progression in non-target lesions, or
- (iii) Date of last radiological assessment of measured lesions (if progression is based on increase in sum of measured lesions).

²An adequate assessment is defined as a radiological assessment where iCR, iPR, or iSD was determined.

Statistical Analysis Plan

SMS-0571/CyPep-1
V3.0 Final
04-Jun-2024

13.4 APPENDIX 4. VISIT ALIGNMENT

Mapping of protocol-defined visits into one common visit set for analysis purposes is presented below in [Table 10](#).

Table 10. Visit Alignment

Visit # (align.)	Visit Label (aligned)	Visit Day	Visit (per protocol)		
			Part I	Part IIa Arms A, B, C	Part IIa Arm D
1	Screening		SCREENING	SCREENING	SCREENING
2	Visit 1 Day 1	1	C1 D1	C1 D1	DAY 1
3	Visit 2 Day 8	8		C1 D8*	DAY 8
4	Visit 3 Day 15	15	C1 D15	C1 D15	DAY 15
5	Visit 4 Day 22	22		C1 D22	DAY 22
6	Visit 5 Day 29	29	C1 D29	C1 D29	
7	Visit 6 Day 36	36	C1 D36	C1 D36	
8	Visit 7 Day 43	43	C2 D1	C2 D1	
9	Visit 8 Day 50	50	C1 D50**		
10	Visit 9 Day 57	57	C2 D15	C2 D15	
11	Visit 10 Day 71	71	C2 D29	C2 D29	
12	Visit 11 Day 78	78	C2 D36	C2 D36	
13	Visit 12 Day 85	85	C3 D1	C3 D1	
14	Visit 13 Day 99	99	C3 D15	C3 D15	
15	Visit 14 Day 113	113	C3 D29	C3 D29	
16	Visit 15 Day 120	120	C3 D36	C3 D36	
17	Visit 16 Day 127	127	C4 D1	C4 D1	
18	Visit 17 Day 141	141	C4 D15	C4 D15	
19	Visit 18 Day 155	155	C4 D29	C4 D29	
20	Visit 19 Day 162	162	C4 D36	C4 D36	
21	Visit 20 Day 169	169	C5 D1	C5 D1	
22	Visit 21 Day 183	183	C5 D15	C5 D15	
23	Visit 22 Day 197	197	C5 D29	C5 D29	
24	Visit 23 Day 204	204	C5 D36	C5 D36	
25	Visit 24 Day 211	211	C6 D1	C6 D1	
26	Visit 25 Day 225	225	C6 D15	C6 D15	
27	Visit 26 Day 239	239	C6 D29	C6 D29	
28	Visit 27 Day 246	246	C6 D36	C6 D36	
29	Visit 28 Day 253	253		C7 D1	
30	Visit 29 Day 267	267		C7 D15	
31	Visit 30 Day 281	281		C7 D29	
32	Visit 31 Day 288	288		C7 D36	
33	Visit 32 Day 295	295		C8 D1	
34	Visit 33 Day 309	309		C8 D15	
35	Visit 34 Day 323	323		C8 D29	
36	Visit 35 Day 330	330		C8 D36	
37	Visit 36 Day 337	337		C9 D1	
38	Visit 37 Day 351	351		C9 D15	
39	Visit 38 Day 365	365		C9 D29	
40	Visit 39 Day 372	372		C9 D36	
41	Visit 40 Day 379	379		C10 D1	
42	Visit 41 Day 393	393		C10 D15	
43	Visit 42 Day 407	407		C10 D29	
44	Visit 43 Day 414	414		C10 D36	
45	Visit 44 Day 421	421		C11 D1	
46	Visit 45 Day 435	435		C11 D15	
47	Visit 46 Day 449	449		C11 D29	
48	Visit 47 Day 456	456		C11 D36	
49	Visit 48 Day 463	463		C12 D1	
50	Visit 49 Day 477	477		C12 D15	
51	Visit 50 Day 491	491		C12 D29	

Statistical Analysis Plan

SMS-0571/CyPep-1

V3.0 Final

04-Jun-2024

Visit # (align.)	Visit Label (aligned)	Visit Day	Visit (per protocol)		
			Part I	Part IIa Arms A, B, C	Part IIa Arm D
52	Visit 51 Day 498	498		C12 D36	
53	Visit 52 Day 505	505		C13 D1	
54	Visit 53 Day 519	519		C13 D15	
55	Visit 54 Day 533	533		C13 D29	
56	Visit 55 Day 540	540		C13 D36	
57	Visit 56 Day 547	547		C14 D1	

13.5 APPENDIX 5. itRECIST DERIVATION RULES

The following section is adopted from (GOLDMACHER, 2020).

For all sum of diameters (SOD) calculations below, lesions that are assessed as “too small to measure” at a specific assessment, are considered to have diameter of 5 mm at that specific assessment (as suggested by RECIST 1.1). In case a lesion is non-evaluable at a timepoint, SOD will be missing for that timepoint.

Timepoint Response: Injected and Non-Injected Target Lesions

For timepoint response per itRECIST, the rules provided in [Table 11](#) below will be used for determining injected and non-injected response.

Table 11. itRECIST Timepoint Response Categories by Lesion Category

itRECIST Response Category	Injected Target Lesions (T-I)	Non-Injected Target Lesions (T-NI)
itCR	All non-nodal lesions gone, nodal lesions <10 mm.	All non-nodal lesions gone, nodal lesions <10 mm.
itPR	≥30% decrease in sum of diameters from last imaging assessment.	≥30% decrease in sum of diameters from baseline.
itPD	≥20% increase in sum of diameters from last imaging assessment (≥5 mm absolute).	≥20% increase in sum of diameters from nadir (≥5 mm absolute).
itSD	Not enough growth for itPD & not enough shrinkage for itPR.	Not enough growth for itPD & not enough shrinkage for itPR.
NE	≥1 lesion cannot be measured.	≥1 lesion cannot be measured or has been injected.

For T-I lesions the response assessment is iterative because lesions selected for injection may vary between visits. At each assessment, the current SOD for all target lesions injected during the previous treatment visit should be compared with their SOD at the previous response assessment. The injected response assessment at given timepoint is based on SOD change from previous assessment.

For T-NI lesions, timepoint responses will only be calculated until the timepoint first T-NI lesion is injected.

Best Response: Injected and Non-Injected Target Lesions

The best response for T-I lesions is determined using the rules provided in [Table 11](#) above, but comparing the SOD based on the smallest size for each injected target lesion to the pre-injection SOD of the same lesions (instead of comparing current results with results from previous assessment).

The best response for T-NI lesions is determined based on non-injected target lesion timepoint responses using the hierarchy of itCR > itPR > itSD > itPD > NE.

Maximum Percent Reduction from Baseline: Injected and Non-Injected Target Lesions

For each T-I lesion, the baseline is its diameter just before it is first injected. Baseline SOD is the sum of all baseline diameters. The best response SOD is the SOD of these lesions at each lesion’s smallest size post-injection. Maximum percent reduction will be calculated as $(\text{Best Response SOD} - \text{Baseline SOD}) / \text{Baseline SOD} \times 100\%$.

For T-NI lesions, the baseline SOD is defined as the SOD of T-NI lesions before any injections. The smallest post-baseline SOD is the smallest SOD observed at any timepoint post-baseline (and before any T-NI lesion becomes injected). The maximum percent reduction will be calculated as $(\text{Smallest Post-baseline SOD} - \text{Baseline SOD}) / \text{Baseline SOD} \times 100\%$.
